4.2.1 Dose escalation rationale

The mTPI2 design is a Bayesian interval design that can be implemented in a simple fashion as the traditional 3+3 design, but it is more flexible and possesses superior operating characteristics. The mTPI2 design provides an upgrade to the modified toxicity probability interval (mTPI) design, with a substantially lower risk of overdosing and a better precision to identify the MTD. The mTPI2 design is applicable for the dose escalations in Part-1 and Part-3A.

The target toxicity rate for the MTD is █, with the acceptable toxicity probability interval of █. At least 3 DLT evaluable participants will be included in each cohort. The decision by the Study Committee in agreement with the Sponsor's Study Medical Manager for dose escalation/de-escalation or stay will be made after the completion of the first cycle of the last DLT evaluable participant at each cohort. The mTPI2 decision rules are based on calculating the unit probability mass (UPM) of intervals as follows: █

Intervals that are lower than █ indicating dose escalation, equivalence interval █ indicating staying at the current dose level, and intervals that are higher than █ indicating dose de-escalation. The interval with the largest UPM will be the winning interval and implies the corresponding dose recommendation. The detailed mTPI2 rules are displayed in [Table 15](#).

When using [Table 15](#), note the following:

- A) If the next dose level is considered to have unacceptable high toxicity, ie, the probability that the DLT rate is larger than █ at the next dose is more than █, then the next enrolled cohort should be kept at current dose and the higher dose will never be used (Decision "DU" in [Table 15](#)).
- B) At any time, if the observed DLT rate at the current dose level is greater than █, then the next enrolled cohort should be de-escalated to the lower dose level, at which the DLT rate is less than █.
- C) If the current dose is the lowest dose and the rule indicates dose de-escalation, treat the new participants at the lowest dose unless there is unacceptable high toxicity, at which point terminate the study for safety. If the decision based on the new cohort at the lowest dose still recommends dose de-escalation, new dose levels may be explored.

- D) If the current dose is the highest dose and the rule indicates dose escalation, treat the new participants at the highest dose. If the decision based on the new cohort at the highest dose still recommends dose escalation, new dose levels may be explored.
- E) If at least 6 participants were treated at the recommended dose level, then this dose level will be the MTD.
- F) Skipping dose is not allowed.

Table 15 - Dose escalation rule of the modified toxicity probability interval-2 method

E: Escalate to the next higher dose, S: Stay at the current dose, D: De-escalate to the next lower dose and the current dose will never be used again because unacceptable high toxicity

a "D" will not be applied for first cohort of dose level 1 as the exception, however "DU" will give priority to the exception, ie, if 3 out of 3 participants have DLT at the dose level 1, the study committee may add lower dose level to assess the safety.

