Part-2 of the study will start once RP2D for SAR442720 from Part-1 is confirmed. The SAR442720 RP2D will be 200 mg BIW, Day 1 and Day 2 of each week, administered orally (21 days per cycle). This dose emerged as the safe dose of SAR442720 from the escalation part (Part-1) of this study. Pembrolizumab will be administered as a dose of 200 mg using a 30 minutes IV infusion on Day 1 every 3 weeks (21 days cycle) or a dose of 400 mg using a 30 minutes IV infusion on Day 1 every 6 weeks (42 days cycle).

The duration of the study for a participant will include:

- Screening period: up to 28 days.
- Treatment Period: enrolled participants will receive continuous treatment until PD, unacceptable AE, other full permanent discontinuation criteria as described in [Section 7.1](#).
- End of Treatment and Follow-up: EOT visit will occur 30 days ± 5 days from last IMP administration or prior to initiation of further therapy. Participants will then enter the Observation period and will be followed differently depending on the reason leading to EOT:

- Participants who discontinue study treatment with radiological or clinical PD (per RECIST v1.1) or iCPD (per iRECIST) will be followed in the Follow-Up Visit 1 occurring 3 months \pm 5 days from last IMP administration, or until start of new anticancer therapy or cohort cut-off, whichever comes first, before moving to the Survival Phone Call Follow-Up Period.

Part-3

Part-3 of this open-label, multi-center, un-controlled, non-randomized study, will assess the safety, RP2D, anti-tumor activity, and PK of SAR442720 in combination with adagrasib in participants with NSCLC harboring KRAS G12C mutation.

Part-3A

SAR442720 and adagrasib will be administered orally on a continuous basis. The starting dose (DL1) of SAR442720 will be 100 mg on Day 1 and Day 2 BIW with adagrasib given at 400 mg BID orally. The dose escalation will follow the mTPI2 design with a minimum of 3 participants evaluable for DLT for each dose level. Participants will be DLT-evaluable if they have taken at least 80% of the scheduled Cycle 1 dose of both drugs in the first 21 days of treatment. The same mTPI-2 design as that used in Part-1 will be used in Part-3A.

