The dose of SAR442720 will be escalated or de-escalated depending on the emerging safety data of the combination. The starting dose (dose level 1 [DL1]) of SAR442720 will be 100 mg BIW, which is 50% of the highest cleared dose in the ongoing Phase 1 monotherapy dose escalation study (<https://clinicaltrials.gov>; NCT03634982). DL2 (140 mg BIW) and DL 3 (200 mg BIW) for SAR442720 have been cleared in the ongoing Phase 1 monotherapy dose escalation study. The adagrasib starting dose (DL1) will be 400 mg BID orally, which is one dose level below the RP2D in monotherapy (3). Refer to [Table 14](#) below for dose escalation. At least 6 participants need to be treated at the MTD and RP2D.

Table 14 - Dose escalation for Part-3A

Dose Level	SAR442720 (BIW)	Adagrasib (daily)
Part-3 – DL(-)1	80 mg D1, D2	400 mg BID
Part-3 – DL1 (starting dose)	100 mg D1, D2	400 mg BID
Part-3 – DL2	140 mg D1, D2	400 mg BID
Part-3 – DL3a ^a	140 mg D1, D2	600 mg BID
Part-3 – DL3b ^a	200 mg D1, D2	400 mg BID
Part-3 – DL4	200 mg D1, D2	600 mg BID

Abbreviations: BID, twice daily; BIW, twice a week; D, day; DL, dose level.

^a DL3b is optional and may be recommended by the study committee according to the safety data before further escalating to DL4.

Overall safety monitoring will be performed throughout the conduct of the study. Additional dose levels and/or additional schedules of administration can be tested based on emerging PK and safety data.

The DLT observation period is 1 cycle (21 days). All the AEs occurring during treatment, unless due to disease progression or to a cause obviously unrelated to IMP, will be taken into consideration by the Sponsor and recruiting Investigators for the determination of the MTD and RP2D for the SAR442720 and adagrasib combination. The Study Committee will review the overall safety, PK/PD, and clinical activity data and in agreement with the Sponsor's Study Medical Manager, will decide the recommended dose for the expansion phase.

The Study Committee will be comprised of the Principal Investigator from each site involved in the dose escalation phase, clinical team members from the Sponsor (including at least the Study Medical Manager, Global Study Manager, and experts when appropriate such as Global Safety Officer, pharmacokineticists, and biostatisticians).

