Using the hypothetical scenarios specified above, the results for mTPI2 are plotted in [Figure 7](#) and [Figure 9](#). The results from 3+3 design are presented in [Figure 8](#) and [Figure 10](#) for a comparison purpose.

In general, mTPI2 design can find the true MTD more accurately than the 3+3 design. The 3+3 design is more conservative than the mTPI2. The chance of finding the correct MTD (in red) is higher than any other dose level for all scenarios in mTPI2 design. While in Scenario 2 and 3, 3+3 design is much conservative to recommend the 100 mg as MTD in more than [REDACTED] of simulated trials. Specifically, when the true DLT rate changes from [REDACTED] in Scenario 2 to [REDACTED] in Scenario 3, the 3+3 design will recommend 100 mg from [REDACTED]. The mTPI2 recommends the 140 mg as MTD consistently ([REDACTED]) in both scenarios. In Scenario 1, the 3+3 design is not able to differentiate 140 mg and 200 mg when the true MTD is 200 mg ([REDACTED]). Even in Scenario 4 where the true MTD is >200 mg, the 3+3 design still identify the MTD as <100 in [REDACTED] of the simulations. Also, when 2 DLTs were observed out of 3 participants, the 3+3 design will claim the MTD has to be lower than the current dose level while the mTPI2 design will just recommend a lower dose level for the next cohort but keep the decision of recommending the current dose level open. Overall, the accuracy of mTPI2 is satisfactory and 3+3 is too conservative.

The sample size needed for both designs are roughly 3 cohorts (9 participants) for all scenarios. But more participants are treated at a dose level below the MTD in 3+3 compared to mTPI2 ([REDACTED]) because 3+3 is too conservative.

[figure not shown]
To conclude, mTPI2 design can provide a more accurate MTD recommendation compared to 3+3 design with similar sample size.

Figure 7 - Probability of a dose level selected as MTD for mTPI2

[figure not shown]
[figure not shown]
Abbreviations: H = high rate of DLT, L = low rate of DLT, MTD = maximum tolerated dose, mTPI2 = modified toxicity probability interval 2, T = target rate of DLT which refers to MTD

Figure 8 - Probability of a dose level selected as MTD for 3+3

Abbreviations: H = high rate of DLT, L = low rate of DLT, MTD = maximum tolerated dose, T = target rate of DLT which refers to MTD

Figure 9 - Mean number of participants per dose level for mTPI2

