#### Part-3

Part-3 of this open-label, multi-center, un-controlled, non-randomized study, will assess the safety, RP2D, anti-tumor activity, and PK of SAR442720 in combination with adagrasib in participants with NSCLC harboring KRAS G12C mutation.

Part-3A of the study will investigate the safety and tolerability of SAR442720 in combination with adagrasib and confirm RP2D. There are 6 dose levels in consideration: the starting dose (dose level 1 [DL1]) of IMP combination will be 100 mg BIW and 400 mg BID for SAR442720 and adagrasib respectively, dose level 2 (DL2) will be 140 mg BIW and 400 mg BID, dose level 3a (DL3a) will be 140 mg BIW and 600 mg BID, dose level 3b (DL3b) will be 200 mg BIW and 400 mg BID, dose level 4 (DL4) will be 200 mg BIW and 600 mg BID, and dose level (-1) ([DL-1]) will be 80 mg BIW and 400 BID. A minimum of 3 DLT evaluable participants for each dose level is required. The DLT observation period is 1 cycle (21 days). The Study Committee will review the overall safety, PK/PD, and clinical activity data and in agreement with the Sponsor's Study Medical Manager, will decide the recommended dose for the expansion phase.

Part-3B dose expansion will assess the anti-tumor activity and safety of SAR442720 combined with adagrasib in participant with NSCLC harboring KRAS G12C mutation. This study will start once RP2D for SAR442720 and adagrasib from Part-3A dose escalation is confirmed. Approximately 40 participants will be enrolled.

Part-4 of this study will assess the effect of food on PK of SAR442720 tablet, when dosed in combination with pembrolizumab in participants with advanced malignancies. It will also evaluate the relative bioavailability of SAR442720 tablet formulation (test) compared to the capsule formulation (reference) when dosed in combination with pembrolizumab. Approximately 12 participants are expected to be enrolled.

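### For 2 DLTs in the first 3 participants at the Part-3A starting dose, Table 15 footnote a points away from de-escalation, rule B very probably points to it, and no text says which prevails

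*Protocol*

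**What the plan says.** Footnote a to Table 15 (Protocol section 4.2.1) makes an exception to decision D: it "will not be applied for first cohort of dose level 1 as the exception". DU takes priority over the exception, and the illustration is: "if 3 out of 3 participants have DLT at the dose level 1, the study committee may add lower dose level to assess the safety".

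Part-3A inherits these rules. Section 4.1 says "The same mTPI-2 design as that used in Part-1 will be used in Part-3A", and section 4.2.1 says "The mTPI2 design is applicable for the dose escalations in Part-1 and Part-3A". Section 4.1 also names the level: "The starting dose (dose level 1 [DL1]) of SAR442720 will be 100 mg BIW", given with adagrasib 400 mg BID. Table 14 places DL(-)1 below it, and SAP section 1.1 agrees: "dose level (-1) ([DL-1]) will be 80 mg BIW and 400 BID".

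Three other texts bear on the same decision:

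- **Rule B (section 4.2.1).** Whenever the observed DLT rate at the current dose passes a limit (blacked out), the next cohort goes to the lower level.
- **Rule C (section 4.2.1).** If D comes up at the lowest dose, new participants stay there unless toxicity is unacceptable. It does not address other levels.
- **Appendix 11 (section 10.11).** In comparing the design with 3+3, it says that "when 2 DLTs were observed out of 3 participants", "the mTPI2 design will just recommend a lower dose level for the next cohort but keep the decision of recommending the current dose level open".

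Section 4.1.2 lets the Study Committee choose the recommended dose or a lower one, and tells it not to choose a dose the model indicates is too toxic.

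**The concern.** The footnote reads as if nothing lay below dose level 1: D is suspended, and a lower level is something the committee might add. In Part-3A a lower level is already on the list. The outcome caught between the rules is 2/3. It is severe enough that the design would ordinarily step down, but on Appendix 11's account it does not close the dose, so DU does not override the footnote.

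This would arise at the first safety decision for a combination in which section 2.3.1.5 expects overlapping gastrointestinal toxicity and up to a 2-fold rise in SAR442720 exposure. A committee that follows the footnote could treat another cohort at DL1 and still be within the written rules. One that follows rule B would move to DL(-)1.

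**Working it through.** **1. The texts applied to 2/3 at DL1 in Part-3A**

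| Text | Result |
|---|---|
| Footnote a | D suspended unless DU applies, so no step down |
| Rule B | Step down if 66.7% exceeds the blacked-out limit, which is very probable |
| Rule C | Not triggered, because DL1 is not the lowest dose; silent on other levels |
| Appendix 11 (general description) | Lower dose for the next cohort, current dose kept open: D, not DU |
| Section 4.1.2 | Committee may go lower; does not rank the rules |

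**2. Is 2/3 D or DU?** The target, interval and DU cutoff are blacked out. Assume a Beta(1,1) prior and a 95% DU cutoff. After x DLTs in 3 the posterior is Beta(1+x, 4−x).

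- After 2/3, Beta(3,2): P(rate > t) = 1 − 4t³ + 3t⁴. This gives 0.973 at t = 0.20, 0.949 at 0.25, 0.916 at 0.30 and 0.892 at 0.33.
- After 3/3, Beta(4,1): P(rate > t) = 1 − t⁴. This gives 0.992 at t = 0.30 and 0.988 at 0.33.
- After 1/3, Beta(2,3): P(rate > t) = (1−t)⁴ + 4t(1−t)³. This gives 0.738 at t = 0.25, 0.652 at 0.30 and 0.599 at 0.33.

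So 3/3 is DU, which reproduces the footnote's example. For targets from 0.25 to 0.33, 2/3 is D and not DU, which matches Appendix 11. At a target of 0.20, 2/3 would be DU and the footnote would not block a step down, but that disagrees with Appendix 11.

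**3. How often would it arise?** P(exactly 2/3) = 3p²(1−p). If D is then suspended and 3 more participants are treated at DL1, the expected extra number at DL1 is 3 × P(2/3).

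| True DLT rate p | P(2/3) | Expected extra at DL1 per trial |
|---|---|---|
| 20% | 0.096 | 0.29 |
| 30% | 0.189 | 0.57 |
| 40% | 0.288 | 0.86 |
| 50% | 0.375 | 1.13 |

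The SAR442720 starting dose is already halved for the possible interaction (section 2.3.1.5), so the lower rows are the more relevant ones.

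**4. What would a repeat cohort at DL1 face?** Under Beta(3,2) the mean rate is 0.60, so 3 × 0.60 = 1.8 DLTs are expected in the next 3. P(no DLT in 3) = (2·3·4)/(5·6·7) = 24/210 = 0.114, so P(at least one) = 0.886.

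**5. Could a clean repeat cohort rescue DL1?** The amendment 01 entry in Appendix 15 mentions a 33% cap on the upper limit of toxicity. That entry is amendment history, so it serves here only as an assumption. Thirteen equivalence intervals with upper bound at or below 0.33 were tried: 0.15–0.25, 0.15–0.30, 0.16–0.33, 0.17–0.25, 0.20–0.25, 0.20–0.30, 0.20–0.33, 0.22–0.28, 0.25–0.30, 0.25–0.33, 0.27–0.33, 0.28–0.33 and 0.30–0.33. The mTPI2 unit-probability-mass rule gives D for 1/3, 2/3 and 2/6 in all 13. With 0.20–0.35 or 0.25–0.35, 1/3 and 2/6 give stay, while 2/3 still gives D.

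**The case against.** **A reader might infer that the protocol forbids de-escalation after 2/3, or forces re-dosing at DL1.** The documents do not support this. Rule B applies at any time, and 66.7% would exceed any plausible limit. Its wording refers to the DLT rate at the lower level, and none has been observed at DL(-)1 after the first cohort, but treating that as a bar would disable rule B whenever the lower level is untried. The committee may also go lower on its own judgement.

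**A reader might also take rule C to prohibit a stay above the lowest dose.** It says only what happens at the lowest dose.

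**Appendix 11's account of 2/3 is general.** It compares mTPI2 with 3+3, and a footnote that calls itself an exception may depart from it. The disagreement with Appendix 11 is therefore weaker than the conflict with rule B.

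**Two harmless readings are open.** Appendix 11 numbers 100 mg, the lowest Part-1 dose, as dose level 1. If the footnote uses that numbering, it largely restates rule C, and its remark about adding a lower level makes sense. Alternatively, the marker may sit only on the 1/3 cell, where D is common under tight intervals and an exception is easier to defend. The Table 15 cells are not visible, so neither reading can be excluded. The footnote text states neither, and Table 14 gives the label DL1 to a dose that is not the lowest. The 3/3 example also suggests that the exception covers everything short of DU.

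**The size rests on assumed thresholds.** With a 90% DU cutoff, 2/3 becomes DU at targets of 0.25 and 0.30, and the footnote would not apply. Appendix 11 favours D, but this is not proof.

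**The problem is not confined to Part-3A.** Part-1 also has DL-1 (100 mg) below DL1 (140 mg). Its RP2D is already selected (section 4.3), so Part-3A is where a correction still helps.

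These points narrow the concern to a conflict of rules. They do not remove it, because nothing says whether the footnote or rule B governs.

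**Conclusion.** The point holds as a conflict between stated rules. For 2/3 DLTs in the first Part-3A cohort, footnote a as worded withholds the step down that rule B very probably requires, although DL(-)1 is already available. At 3/3 there is no conflict, only loose wording about adding a level that exists.

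At true DLT rates of 20% to 30% the situation has a 9.6% to 18.9% chance of arising. It would put on average 0.29 to 0.57 more participants at DL1 per trial, and only if the committee followed the footnote rather than rule B or its own discretion. When it does arise, DL1 looks poor: under a flat prior there is a 92% probability that the DLT rate exceeds 30%, and an 89% chance of at least one DLT in the next 3.

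The binomial figures depend only on the assumed true rate. The others also depend on the assumed prior and, for the D/DU classification, on the assumed target, interval and cutoff. Confidence is medium because the marked Table 15 cell cannot be seen. The severity is a minor to moderate wording correction to a safety rule.

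**What to change.** Limit footnote a to the lowest planned dose level or, if that was the intent, to 1/3 DLTs. Then state for Part-3A that 2/3 at DL1 sends the next cohort to DL(-)1, and that 3/3 sends it to DL(-)1 with DL1 closed. The second statement replaces the remark about possibly adding a lower level. Optionally, relabel the Appendix 11 doses as DL-1, DL1 and DL2 to match Table 13.

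The cost is a short edit to one footnote. Sample size and schedule do not change.

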4.3 JUSTIFICATION FOR DOSE

Part-1 (SAR442720)

The starting dose of SAR442720 is selected based on ongoing clinical trials. The starting dose of SAR442720 is 140 mg Day 1 and Day 4 BIW, [REDACTED]

[REDACTED] Please refer to RMC 4630 IB for more details. Given the overall safety profile based on the available clinical data on pembrolizumab and SAR442720 monotherapy, the starting dose of SAR442720 in this combination study is 140 mg administered orally BIW (Day 1 and Day 4 schedule) in a 21-day cycle. During the study, alternative BIW dose schedules, such as Day 1 and Day 2 of each week, or any other emergent dose schedule from the ongoing Phase 1 monotherapy escalation study can be explored after agreement of the Study Committee.

Part-2 (SAR442720)

Part-2 of the study will start once RP2D for SAR442720 from Part-1 is confirmed. The dose of SAR442720 in Part-2 will be the RP2D, which will be the highest cleared dose from Part-1 which will most likely be 200 mg BIW, such as D1 and D2 of each week.

The dose of pembrolizumab for Part-1 and Part-2 is the fixed recommended dose of 200 mg IV Q3W or 400 mg IV Q6W.

Part-3 (SAR442720 and adagrasib)

The starting dose of SAR442720 is selected based on the preliminary clinical safety and tolerability observed in Phase 1 RMC-4630-01 monotherapy study. A dose of 200 mg BIW Day 1 Day 2 SAR442720 has been cleared by the Dose Committee and selected as the RP2D for the final expansion cohort. SAR442720 is identified as a CYP3A and P-gp substrate, with CYP3A contributing to approximately [REDACTED] of total hepatocyte metabolism. Adagrasib is a strong inhibitor of CYP3A and a weak inhibitor of P-gp, which may increase SAR442720 exposure up to [REDACTED] (mainly due to CYP3A inhibition). Therefore, the starting dose of SAR442720 is selected to be [REDACTED] less than the RP2D at monotherapy, which is 100 mg Day 1, Day 2 (D1D2).

SAR442720 is not anticipated to alter the PK of adagrasib.

Part-4 (SAR442720)

Part-4 of the study will start at the RP2D for SAR442720 from Part-1, the highest cleared dose from Part-1, which is 200 mg BIW, administered on D1 and D2 of each week. This dose has been cleared by the Dose Committee and selected as the RP2D for the combination of SAR442720 and pembrolizumab.

The dose of pembrolizumab for Part-4 is the fixed recommended dose of 200 mg IV Q3W or 400 mg IV Q6W.

4.4 END OF STUDY DEFINITION

The end of the study is defined as the date of the last visit of the last participant in the study or last scheduled procedure shown in the Schedule of Activities for the last participant in the trial globally.

5 STUDY POPULATION

Prospective approval of protocol deviations to recruitment and enrollment criteria, also known as protocol waivers or exemptions, is not permitted.

5.1 INCLUSION CRITERIA

Participants are eligible to be included in the study only if all of the following criteria apply:

Age

I 01. All participants must be ≥ 18 years of age (or country's legal age of majority if > 18 years), at the time of signing the informed consent.

Type of participant and disease characteristics

I 02. Part-1 and Part-4 participants should have histologically or cytologically proven diagnosis of non-squamous NSCLC with metastatic disease progression after platinum-based chemotherapy and ICI irrespective of the sequence, ie, either concurrently or sequentially:

- At least one prior line of treatment in a metastatic setting
- Relapse to develop metastatic disease during or within 6 months of an adjuvant/neoadjuvant treatment (to be considered as first-line treatment), OR
- Disease progression after or during one platinum-based chemotherapy and one ICI (anti-PD1/PD-L1) irrespective of the sequence, ie, concurrently or sequentially.

OR

Histologically proven diagnosis of advanced solid tumors including CRC that have failed, are intolerant to or are considered ineligible for SoC anti-cancer treatments including approved drugs for oncogenic drivers in their tumor type.

I 03. Part-1 participants must have one or more of the following molecular aberrations:

- KRAS^{G12C} mutations (NSCLC, CRC and any other histotype)
- KRAS^{G12A}, KRAS^{G12D}, KRAS^{G12S}, KRAS^{G12V} mutations (NSCLC)
- KRAS^{G12A}, KRAS^{G12D}, KRAS^{G12S}, KRAS^{G12V} and/or MSI-H or dMMR (CRC)
- KRAS amplification (any histotype)
- NF1 LOF (any histotype)
- BRAF Class 3 mutations (any histotype)

I 04. All participants should have at least 1 measurable disease per RECIST v1.1. An irradiated lesion can be considered measurable only if progression has been demonstrated on the irradiated lesion.

I 05. All participants should have Eastern Cooperative Oncology Group (ECOG) performance status 0-1.

Sex

I 06. All (male or female) participants

Contraceptive use by men or women should be consistent with local regulations regarding the methods of contraception for those participating in clinical studies.

a) Male participants

A male participant must agree to use contraception (see Appendix 4 [[Section 10.4](#)]) during the intervention period and for at least 4 months (6 months for Part-3) after the last dose of study intervention.

b) Female participants

A female participant is eligible to participate if she is not pregnant (see Appendix 4 [[Section 10.4](#)]), not breastfeeding, and at least one of the following conditions applies:

- Not a woman of childbearing potential (WOCBP) as defined in Appendix 4 [[Section 10.4](#)]).

OR

- A WOCBP who agrees to follow the contraceptive guidance in Appendix 4 [[Section 10.4](#)]) during the intervention period and for at least 4 months (6 months for Part-3) after the last dose of study intervention.

Informed Consent

I 07. All participants should be capable of giving signed informed consent as described in Appendix 1 of the protocol which includes compliance with the requirements and restrictions listed in the informed consent form (ICF) and in this protocol.

Part-2 (new criteria added with amendment 03)

I 08. Cancer diagnosis at study entry:

For participants in Cohorts A, - histologically or cytologically confirmed diagnosis of Stage IV (per American Joint Committee on Cancer [AJCC] 8th edition [112]) NSCLC.

I 09. For Part-2, PD-L1 expression TPS as determined (with an absolute value provided to Sponsor) at local laboratory.

- Cohort A1: PD-L1 expression TPS $\geq 50\%$,
- Cohort A2: PD-L1 expression TPS 1%-49%.

I 10. Provision of tumor tissue:

- Mandatory for participants enrolled with local PD-L1 testing. Baseline tumor tissue or slides should be provided for central lab retrospective analysis. Archival tumor tissue samples should be obtained from biopsies done within 6 months, and there should be no systemic anti-cancer therapy between collection of biopsy and enrollment. Slides specifications are detailed in Lab Manual.

I 11. Prior anticancer therapy

- For participants in Cohorts A1 and A2 - Have not received prior systemic therapy for advanced/metastatic NSCLC. Participants who received adjuvant or neoadjuvant therapy are eligible if the adjuvant/neoadjuvant therapy was completed at least 6 months prior to the development of metastatic disease.

Part-3 (new criteria added with amendment 04)

I 12. Participants with histologically or cytologically proven metastatic NSCLC with at least one prior line of treatment in a metastatic setting. Prior KRAS G12C targeted therapy is acceptable (only in Part-3A)

I 13. Participants must have following molecular aberration tested at the local laboratory:

- KRAS G12C mutation assessed by a local Sponsor-approved test. Approved test list can be found in eCRF.

